4 ANALYTICAL METHODS

4.1 Codebook Development

Thematic analysis methods will be used to analyze the interview transcript data ([Braun and Clarke, 2006](#)). An initial coding framework (Draft 1; 25 February 2020) based on the final interview guide is presented in [Appendix B](#). Finalization of the codebook will be an iterative process based on the interview data. Specifically, it is anticipated that new codes will be added to the codebook as new concepts (e.g., potential DPNP symptoms, impacts) are identified during transcript review.

4.2 Transcript Coding

Each interview transcript will be coded in accordance with the codebook. To ensure consistency in coding, approximately 10% ($n = 6$) of the transcripts will be double coded, meaning that two different people will code these transcripts. Any discrepancies found between these codes will be resolved by the two coders and in discussion with the Project Director.

4.3 Qualitative Data Analysis

Standardized qualitative research methods will be applied during the conduct of each interview ([Willis, 1999](#); [Boeije, 2002](#)). Specifically, immediately following the receipt of each transcript, RTI-HS will begin the thematic analysis process. Using field notes and transcripts, thematic analysis methods will be used to analyze the interview transcript data. Important concepts and dominant trends will be identified in each interview. These individual interview results will then be compared across interviews to allow for the

generation of themes or patterns in interview participants' responses. As noted above, the qualitative data analyses will be facilitated through the use of ATLAS.ti and other software (e.g., Microsoft Excel).

4.4 Quantitative Data Analysis

The ATLAS codebook ([Appendix B](#)) includes codes to facilitate quantitative summarization (descriptive analysis) of interview participants' reports related to DPNP symptoms and impacts. In the analysis and reporting of frequencies or counts of these concepts, only unique mentions per code per patient will be counted.

- Frequency and percentage of interview participants reporting each DPNP symptom/sensation before the clinical trial
- Frequency and percentage of interview participants reporting pain in specific locations (e.g., hands, arms, feet)
- Frequency and percentage of interview participants reporting a specific location (e.g., hands, arms, feet) as the location where their pain is most severe
- Frequency and percentage of interview participants reporting a specific location (e.g., hands, arms, feet) as the most bothersome
- Frequency and percentage with which each symptom or sensation was reported as the most bothersome
- Frequency and percentage of DPNP impacts reported before the clinical trial
- Frequency and percentage of a DPNP symptom being reported as the most important to treat prior to starting the clinical trial

Descriptive statistics (frequencies, mean, range) will be computed for the following assessments for the overall interview sample and by treatment assignment, as provided by Lexicon (LX9211 treatment [10 mg or 20 mg] or placebo):

- Clinical and demographic characteristics reported (e.g., sex, age, age of diagnosis of diabetes, age at onset of DPNP symptoms)
- Frequency and percentage of interview participants reporting specific symptom improvements during the clinical trial
- Frequency and percentage of improvement in a symptom (reported during the clinical trial) being reported as the most important improvement
- Frequency and percentage of specific impacts of symptom improvements being reported across interview participants

- Satisfaction with treatment before and after the clinical trial
 - 0 = not at all satisfied, 1 = a little satisfied, 2 = moderately satisfied, 3 = quite satisfied, and 4 = very satisfied
- Difficulty managing DPNP before the clinical trial
 - 0 = not at all difficult, 1 = a little difficult, 2 = moderately difficult, 3 = quite difficult, 4 = very difficult
- Ratings for how important it would be for a treatment to improve specific symptoms
 - 1 = not at all important, 2 = a little important, 3 = moderately important, 4 = very important, 5 = extremely important
- Importance ratings for any symptom reported as improved during the clinical trial
 - 1 = not at all important, 2 = a little important, 3 = moderately important, 4 = very important, 5 = extremely important
- Preference of study drug or a previous medication
- Desire to continue study drug (yes/no)

As noted previously, analysis will initially be conducted on blinded data, and will be presented in aggregate in the first draft of the summary report ([Section 5](#)). After provision of the treatment assignment data (from Lexicon) RTI-HS will conduct analyses by treatment group.

For the analysis correlating/examining the relationship between selected interview (e.g., treatment satisfaction, desire to continue on treatment and treatment preference) and clinical trial results (e.g., baseline average daily pain score and the change in average daily pain score; up to 5 variables, to be decided in collaboration with Lexicon), it is anticipated that Lexicon will provide RTI-HS with clinical data in one of two formats:

- Clinical Data Interchange Standards Consortium (CDISC)-compliant data sets in SAS Analysis Data Model (ADaM) format
 - OR
- A SAS data set organized as one row per patient and structured such that a variable measured at multiple time points is represented as multiple variables (columns) per patient (rather than multiple observations or rows per patient).

Lexicon will also provide RTI-HS with codebooks and any other relevant data documentation and will be available to answer questions regarding the data and appropriate analysis variables.

5 REPORTING

RTI-HS will prepare and submit to Lexicon a summary report describing the interview methods and results. The draft report will be prepared using blinded data; the final summary report will incorporate treatment assignment provided by Lexicon. Specifically, this report will include results pertaining to each of the research questions outlined in [Section 2](#). Tables will be prepared to summarize the results of the descriptive analyses outlined in [Sections 4.3](#) and [4.4](#). Table shells for use in the final report are provided in [Appendix C](#) (these same shells will be used to inform the draft report; however, data will be presented in aggregate on blinded data).

Although adverse event elicitation and description are not an objective of this study, any adverse events (as described in the study procedure guide) reported in the context of the patient interviews will be summarized in tabular format in the summary report. Sites will be notified of any reported adverse events, and all reported events will be reconciled by Lexicon or their designee with the clinical trial safety database to ensure no new signals were detected.

Appendix A. Final Interview Guide

Phase 2 Clinical Trial of LX9211 for the Treatment of Diabetic Peripheral Neuropathic Pain

Exit Interviews

I. Introduction	~ 5 min
------------------------	----------------

[Introduce interviewers; confirm participant's first name before starting the interview; confirm with the participant that now is still a convenient time for the interview—if the patient expresses any concerns or hesitancy (or based on the interviewer's judgment), reschedule the interview.]

[Remind participant about key elements listed in consent form]

The purpose of today's interview is to learn more about your experiences, specifically:

- Your experiences with diabetic peripheral neuropathic pain (we will refer to this as neuropathic pain) and its treatments
- Any expectations about the study drug you had before starting the clinical trial
- Your experiences with the drug you received in the clinical study and
- Any improvements you may have noticed from the study drug.

The information you provide today will be used to help the study sponsor better understand people's experiences with nerve pain associated with their diabetes and their experiences with the study drug.

We invite you to speak openly and share your opinions freely. We value everything you tell us and be assured that there are no wrong answers.

This information is in the study consent form, but as a reminder...

- Our discussion today is scheduled to take about 60 minutes.
- We are audio recording and transcribing all interviews to make sure we do not miss any important information. Also, this will help us write a summary report.
- The transcripts from the interviews will be given to the study sponsor at the end of this study, with only your study ID number attached. All names mentioned during the interview will be removed from the transcript.
- Finally, please remember that today's interview is completely voluntary; you can take a break or end the discussion at any time.

If you report a side effect during today's call that is potentially related to the study drug, I will have to notify your clinical site. They will determine whether your study doctor needs to follow-up with you for more information.

Additionally, the clinical study sponsor will share limited data from the clinical study with us so that we can better understand experiences of participants in the study. For example, they may share with us scores from some of the questionnaires you completed as part of the clinical study and your responses to certain questions about how well the drug worked for you.

Do you have any questions before we begin? [\[Answer any questions.\]](#)

START RECORDING

[Once the recording starts, the interviewer will verbally record the participant's clinical study ID and interview date for the audio]

We have started the audio recording. Do we have your permission to continue with the interview?

Yes → [CONTINUE](#)
 No → [STOP INTERVIEW](#)

II. Background Information and Prestudy Experiences **~ 10 min**

[RECORD]

First, I would like to learn a little more about you and about your experiences with diabetic neuropathic pain

1. **How old are you? _____ years** [\[Confirm from recruitment grid\]](#)
2. **About how old were you when you were diagnosed with diabetes?**
_____ (years old)
3. **About how long ago did you start to experience neuropathic pain associated with your diabetes?** _____ (months/years)

4. Before starting the study, in your own words, what did this pain feel like?

[If not reported spontaneously probe for the presence of the following]

- a) Numbness/dead feeling**
- b) Tingling/pins and needles**
- c) Weakness**
- d) Very sensitive/heightened sensitivity to touch and pressure**

5. Before starting the study, where did you experience your neuropathic pain?

- a) Hands**
- b) Arms**
- c) Feet**
- d) Legs**
- e) Other** _____

6. [If experienced in more than 1 location] Were there specific locations where the pain was more severe than others before starting the clinical trial? [If yes] Which ones?

7. [If more than one symptom experienced] Were specific symptoms more bothersome to you than others before starting the clinical trial? [If necessary, remind patient of the symptoms reported in Q4]. [If yes] Which ones?

8. Before starting the clinical trial, overall, how satisfied were you with your neuropathic pain treatment(s)?

- 0 = Not at all satisfied
- 1 = A little satisfied
- 2 = Moderately satisfied
- 3 = Quite satisfied
- 4 = Very satisfied

- Tell me why you selected that answer.

9. **Before starting the clinical trial, how easy or hard was it for you to manage your neuropathic pain?**

0 = Not at all difficult
 1 = A little difficult
 2 = Moderately difficult
 3 = Quite difficult
 4 = Very difficult

- Tell me why you selected that answer.

III. Prestudy Impact/Burden Of DPNP	~ 10 min
--	-----------------

10. **Before starting the study, what impact did diabetic neuropathic pain have on your life, if at all? [Allow for spontaneous reports of impacts. Specific probes are listed below]**

11. **How, if at all, did this pain affect your life before the study? [Probe for impact areas if not spontaneously reported]...**

- a) Daily activities? What kinds of daily activities were impacted?
 - Are there things you could not do because of the pain that you wanted to do?
- b) Mobility (e.g., walking; using stairs; getting up/down from chair or toilet)
- c) Mood/emotions (e.g., depressed mood, anxiety, irritability, anger)
- d) Self-care (e.g., bathing or dressing self; using utensils)
- e) Sleep

12. **What was it about your neuropathic pain or its treatment that bothered you the most before starting the study? [Probe to understand if most bothersome issues are issues related to the pain and/or are treatment-related]**

Why does [repeat most bothersome issue] bother you?

IV. Prestudy Treatment Expectations

~ 5 min

13. Thinking back to before you started the clinical trial, what were some of the reasons you decided to participate in the trial?
 - a) Were some reasons more important to you than others? **[If yes]** Which ones?
14. Before starting the clinical trial, were there specific symptoms/problems that you most wanted the study drug to help? Which ones? Why?
15. How important to you would it be for a neuropathic pain treatment to improve? **[Use the 1-to-5 rating scale below for each symptom the patient reports – examples listed below. Repeat scale as often as needed]**
 - 1 = Not at all important
 - 2 = A little important
 - 3 = Somewhat important
 - 4 = Very important
 - 5 = Extremely important
 - a) Pain
 - b) Numbness
 - c) Tingling/pins and needles
 - d) Weakness

V. During Study Experiences

~ 15 min

Now I would like to talk to you about your experiences during the clinical study. So, thinking about your experiences while you were taking the study drug....

- 16. What were your overall impressions of the study drug?**

- 17. What improvements, if any, did you notice while taking the study drug?**
[Ask the participant to describe each improvement reported. Allow for spontaneous reports of improvements in symptoms/pain. If not already mentioned, probe to see if the symptoms experienced before the study improved, if so, have the participant describe the improvement and rate the importance of the improvement below]

- 18. Please rate the importance of the improvement in [SYMPTOM from Q4] on the following scale (from 1 to 5). I will read the scale to you:**

 1 = Not at all important
 2 = A little important
 3 = Moderately important
 4 = Very important
 5 = Extremely important

Why?

[If improvements noticed] How soon after receiving the study drug did you notice these improvements?

- a) What, specifically, did you notice first?

VI. Impact of Improvements [If no improvements, skip to Q 23] ~ 10 min

19. Thinking about the improvements [Refer back to improvements listed above] you noticed as a result of the study drug, which are the most important to you? Why?
20. Thinking about the improvements you have seen from the study drug; how did these improvements affect you in your daily life? [Allow for spontaneous responses]

[If not reported spontaneously] How, if at all, did these improvements affect your...

- a) Daily activities? What kinds of daily activities were impacted?
 - Are there things you can now do or do better because of improvements in neuropathic pain?
- b) Mobility (e.g., walking; using stairs; getting up/down from chair or toilet)
- c) Mood/emotions (e.g., depressed mood, anxiety)
- d) Self-care (e.g., bathing or dressing self; using utensils)
- e) Sleep

21. You mentioned that that [insert response from Q14] bothered you the most. How, if at all, did the study drug improve these issues?

VII. Treatment Satisfaction and Preference

~ 5 min

22. Overall, how satisfied are you with the study drug as a treatment for diabetic neuropathic pain?

- 0 = Not at all satisfied
- 1 = A little satisfied
- 2 = Moderately satisfied
- 3 = Quite satisfied
- 4 = Very satisfied

- a) Tell me why you selected that response. [Probe to better understand what specifically influenced participant's response to this question]

23. Thinking about the study drug compared to the neuropathic pain treatment(s) you had tried before the study, which did you prefer:

- Study drug
- A previous medication

Why?

24. Would you have continued taking the study drug if you could have?

- Yes
- No

Why?

VIII. Summing Up

~ 2 min

Thank you for sharing your thoughts and experiences with us today. This information is very valuable and will help the study sponsors understand more about patients with diabetic neuropathic pain and the impact of the study drug.

Is there anything else you think we should know (i.e., anything we should have asked but didn't)?

[Thank participant again and end call]

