9.1 Definitions and Special Considerations

9.1.1 Adverse Events

An AE is defined as any untoward medical occurrence associated with the use of a drug in humans, whether or not considered drug related.

Non-serious AE collection will be initiated after the first dose of double-blind study drug.

Any sign, symptom, or illness occurring prior to the first dose of double-blind study drug will be captured in the medical history. Treatment-emergent adverse events are defined as any AEs reported after the first dose of double-blind study drug.

An AE includes any noxious, pathological, or unintended change in anatomical, physiological, or metabolic functions as indicated by physical signs or symptoms occurring after a patient has provided informed consent, whether or not considered related to the study medication.

This definition includes an exacerbation of preexisting medical conditions or events, historical conditions not present prior to study treatment, which reappear following study treatment, intercurrent illnesses, hypersensitivity reactions, drug-drug or drug-food interactions, medication errors, overdose (both intentional or unintentional), drug misuse/abuse, false positive laboratory test, or the significant worsening of the disease under investigation.

Anticipated day-to-day fluctuations of preexisting conditions that do not represent a clinically significant exacerbation or worsening need not be reported as AEs.

Treatment-emergent AEs are defined as any AEs reported after the first dose of double-blind study medication on study Day 1.

Any treatment-emergent abnormal laboratory result should be reported as an AE if it meets 1 or more of the following conditions:

- Fulfills any of the criteria for an SAE (Section 9.1.2),
- Results in discontinuation of study treatment,
- Requires treatment,
- Is considered by the Investigator to be clinically significant.

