9.2.2 Causality

Causality assessment is a determination of whether there is a reasonable possibility that the study medication caused an AE. Factors that should be considered in causality assessment include, but are not limited to, temporal relationship, dechallenge/rechallenge information, association (or lack of association) with underlying disease or concomitant medication, biological plausibility, and previous observation or lack of with the study medication or other medication(s) in the same class as the study medication.

For each AE, the Investigator will assess the causal relationship between the study medication and the AE using their clinical expertise and judgment according to the most appropriate description as follows:

- Not related: The AE does not follow a reasonable temporal relationship to administration of the study medication, or an alternative etiology (eg, underlying disease, complications, concomitant drugs, or concurrent treatment) is much more likely
- Unlikely related: The AE has an improbable temporal relationship to administration of the study medication, or an alternative etiology (eg, underlying disease, complications, concomitant drugs, or concurrent treatment) is more likely
- Possibly related: The AE follows a reasonable temporal relationship to administration of the study medication (including the course after withdrawal of the drug), and an alternative etiology (eg, underlying disease, complications, concomitant drugs, or concurrent treatment) is equally or less likely
- **Probably related**: The AE follows a reasonable temporal relationship to administration of the study drug (including the course after withdrawal of the drug), and an alternative explanation (eg, underlying disease, complications, concomitant drugs, or concurrent treatment) is unlikely
- **Definitely related**: The AE follows a plausible temporal relationship to administration of the study medication (including the course after withdrawal of the drug) and alternative etiology (eg, underlying disease, complications, concomitant drugs, or concurrent treatment) can be ruled out. Positive rechallenge (ie, reappearance or worsening of the AE after the study drug is reintroduced) or a response pattern known to be associated with administration of the study drug provides further evidence of a definitive causality assessment.

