9.4 Reporting of Serious Adverse Events and Pregnancies

All SAEs, regardless of causal relationship to the study medication, and pregnancies must be reported to the Sponsor within 24 hours of investigational site awareness of the event. Investigators should not wait for complete information on an event before notifying the Sponsor (or designee) of an SAE.

Investigational site personnel must use the SAE Report form and Pregnancy form provided by the Sponsor to report these events.

The SAE form should be sent to:

Safety Data [contact] or

Email address (in case of fax failure): [contact]

In case of failure of/lack of access to both email and fax, the event should be reported using Physician On-Call [contact].

If an SAE is reported via telephone, the telephone report should be followed by a completed SAE Report form.

For questions on safety reporting, the Safety Physician of the study should be contacted at:

MD
Drug Safety Physician
Email:
Phone:

For questions on study patient management related to AE, the Medical Monitor of the study should be contacted.

Where applicable, information from relevant hospital records and autopsy reports should be obtained.

Additional information received after the initial SAE has been reported to the Sponsor should be reported as follow-up information following the same procedure and timeline as the initial SAE.

All SAEs, pregnancies, and other special situations should also be recorded on the study patient's eCRF page for AEs.

An SAE that occurs after completion of the study and in the opinion of the Investigator, is related to the study medication should be reported following the same procedure and timeline as an SAE that occurs during the study.

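### The exit-interview script ties site notification to possible drug-relatedness, while Section 5 of the same plan and the protocol's safety rules set no such condition

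*SAP*

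**What the plan says.** **Interview script** (qualitative plan, Appendix A, Introduction). The condition for telling the site is that the patient reports a "side effect during today's call that is potentially related to the study drug, I will have to notify your clinical site". The script then says of the site: "They will determine whether your study doctor needs to follow-up with you for more information". No other sentence in the guide tells the interviewer what to do with an adverse event.

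**Reporting section of the same plan** (Section 5). Here the rule is unconditional: "Sites will be notified of any reported adverse events, and all reported events will be reconciled by Lexicon or their designee", the comparison being with the trial safety database. The summary report is also to carry a table: "any adverse events (as described in the study procedure guide) reported in the context of the patient interviews will be summarized in tabular format". The study procedure guide named there is not among the documents.

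**Protocol.** Section 9.1.1 states: "An AE is defined as any untoward medical occurrence associated with the use of a drug in humans, whether or not considered drug related". Section 9.2.2 says that for every event "the Investigator will assess the causal relationship between the study medication and the AE", on a scale whose lowest grades are not related and unlikely related. Section 9.4 adds: "All SAEs, regardless of causal relationship to the study medication, and pregnancies must be reported to the Sponsor within 24 hours", counted from the site's awareness of the event. Section 8.1.5, which describes the interview, gives the interviewer no rule for adverse events.

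**The concern.** The two passages of the qualitative plan send different sets of events to the site. The narrower wording is in the text that the interviewer reads aloud to every patient.

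If the script is taken as the working instruction, someone on a telephone call decides whether an event might be drug-related before the site hears of it. The protocol places that decision with the Investigator, after the event has been recorded. SAP Section 7.7.2 relies on that order. It tabulates treatment-emergent events as related and unrelated, and it counts an unknown or missing relationship as drug-related. A screen at the interview works in the opposite direction, because an event held back as unrelated enters neither column.

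What is at stake is the completeness and timeliness of safety reporting for the interviewed patients, who include those who left treatment early.

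**Working it through.** No statistical figure is involved, so the check is a comparison of texts, a timing check and a coverage calculation.

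**1. Which events go to the site?**
- Script (Appendix A): side effects that are potentially related to study drug.
- Section 5: any adverse event reported in an interview.
- Protocol 9.1.1 and 9.4: adverse events are defined, and serious ones reported, without regard to relatedness.

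The script names a subset of what Section 5 names. An interviewer who forwards everything satisfies both texts. An interviewer who forwards only what the script names falls short of Section 5.

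**2. Who judges relatedness?**
- Script: the sentence is in the interviewer's first person, and the condition has to be settled before the site is told. The site's stated task afterwards is to decide on follow-up by the study doctor.
- Protocol 9.2.2: the Investigator, for each event.

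**3. Does the rest of the qualitative plan implement Section 5?**
- The draft codebook (Appendix B, codes 1.0 to 10.3) has no adverse-event code.
- The table shells (Appendix C, Tables C-1 to C-20) include no adverse-event table, although Section 5 promises one.
- Interviews are recorded and transcribed, a second transcriptionist checks each transcript, and the technical team reviews transcripts during coding (Section 3.1). The script says the sponsor receives the transcripts when the study ends. An event the patient mentions is therefore on record, but this is a slow route.

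**4. Timing.** Interviews fall within 2 weeks of the Week 6 or early-withdrawal visit (Protocol 8.1.5 and Appendix A), or within 2 to 3 weeks according to Figure 5.1-1.
- For a completer, the latest is Week 6 + 2 = Week 8, or Week 6 + 3 = Week 9.
- Adverse-event collection runs through the Week 11 visit, and the schedule shows no clinic visit between Weeks 6 and 11.

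An interview held on schedule is thus inside the collection window, with one site visit still to come 2 to 3 weeks or more later (11 − 9 = 2; 11 − 8 = 3). For an early withdrawal, the corresponding visit is 35 days after that visit.

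**5. Coverage.** Protocol Section 6 plans 60 to 85 interviews, 282 patients and a maximum of 351.
- 60/282 = 21.3% and 85/282 = 30.1%.
- 60/351 = 17.1% and 85/351 = 24.2%.

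These are shares of patients interviewed. The documents give no rate of events mentioned in interviews or of events judged unrelated, so the number affected cannot be calculated.

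**The case against.** The best case for the plan is that the sentence is a disclosure to the patient and not a procedure. It sits among introductory reminders and states one circumstance in which the interviewer must contact the site. It does not say that other events are withheld. The operating rule is Section 5, which is unconditional and backed by reconciliation with the safety database. Eliciting adverse events is not an aim of the interviews. Sites ask about them at every visit through Week 11, and the Investigator's duties are unchanged. The study procedure guide may already instruct interviewers correctly.

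Most of this stands, and it rules out several stronger readings that a reader might infer:

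- *Only possibly related side effects reach the site.* The word *only* is not in the script, and Section 5 says the opposite.
- *Patients are told that unrelated problems are of no interest.* The script says nothing of the kind. It invites patients to speak openly and says that everything they tell is valued.
- *Events are lost from the safety data.* No loss is shown. Section 5, the transcripts and the Week 11 visit could each recover an event.
- *The interviewer must forward possible serious events the same day.* No passage sets a deadline for the vendor. The 24-hour rule in Protocol 9.4 runs from the site's awareness.

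The objection does not remove the mismatch. It shows which text should prevail, but the interviewer has the other one in hand. The procedure guide cannot be assumed to cure the conflict, since its content is unknown here. The protocol's duties fall on the Investigator and the site, which is why a screen placed ahead of them matters.

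**Conclusion.** The point holds as a mismatch in safety-reporting wording. The script makes notification conditional on potential relatedness; Section 5 of the same plan does not, and the protocol leaves causality to the Investigator. The consequence is a risk that an event mentioned on the call is forwarded late or not at all.

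That risk assumes that at least some interviewers work from the script and not from Section 5, and that the study procedure guide does not already override the script. Neither assumption can be tested from the documents. The exposure is bounded by the interviewed share in the coverage calculation, and the share affected is unknown. The missing adverse-event code and table shell add to the point, because Section 5 then has no visible implementing step in the plan's own appendices. The primary and secondary efficacy analyses are untouched.

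**What to change.** Replace the conditional sentence in the interview guide with one that matches Section 5, for example: *If you mention any side effect or health problem on this call, whether or not it might be connected with the study drug, I will pass it to your clinical site.* Add an instruction that the interviewer does not judge relatedness. Check that the study procedure guide says the same.

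Add an adverse-event code to the codebook in Appendix B and, in Appendix C, a shell for the adverse-event table that Section 5 promises.

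The cost is one sentence, a short interviewer briefing, one code and one table shell. The downside is that sites receive a few more events to assess, some of which they will already have recorded.
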